12. DATA REPORTING / REGULATORY REQUIREMENTS

Adverse event lists, guidelines, and instructions for AE reporting can be found in Section 7.0 (Adverse Events: List and Reporting Requirements).

12.1 Data Reporting

12.1.1 Method

The ODQ will collect, manage, and perform quality checks on the data for this study.

12.1.2 Responsibility for Data Submission

Investigative sites within DF/HCC or DF/PCC are responsible for submitting data and/or data forms to the ODQ according to the schedule set by the ODQ.

Form	Submission Timeline
Eligibility Checklist	Complete prior to registration with ODQ
On Study Form	Within 14 days of registration
Baseline Assessment Form	Within 14 days of registration
Treatment Form	Within 10 days of treatment administration
Adverse Event Report Form	Within 10 days of AE assessment/notification
Response Assessment Form	Within 10 days of response assessment
Off Treatment/Off Study Form	Within 14 days of completing treatment or being taken off study for any reason
Follow up/Survival Form	Within 14 days of the protocol defined follow up visit date or call

12.2 Data Safety Monitoring

The DF/HCC Data and Safety Monitoring Committee (DSMC) will review and monitor toxicity and accrual data from this study. The committee is composed of clinical specialists with experience in oncology and who have no direct relationship with the study. Information that raises any questions about participant safety will be addressed with the Overall PI and study team.

The DSMC will review each protocol up to four times a year or more often if required to review toxicity and accrual data. Information to be provided to the committee may include: up-to-date participant accrual; current dose level information; DLT information; all grade 2 or higher unexpected adverse events that have been reported; summary of all deaths occurring with 30 days of intervention for Phase I or II protocols; for gene therapy protocols, summary of all deaths while being treated and during active follow-up; any response information; audit results, and a summary provided by the study team. Other information (e.g. scans, laboratory values) will be provided upon request.

12.3 Multicenter Guidelines

N/A

12.4 Collaborative Agreements Language

N/A

13. STATISTICAL CONSIDERATIONS

This is a single arm phase II trial to investigate the therapeutic effect of ipilimumab and nivolumab in leptomeningeal carcinomatosis.

13.1 Study Design/Endpoints

Primary endpoint: Rate of overall survival at 3 months

Secondary Endpoints:

1. Toxicity by CTCAE criteria (grade 3 or higher hematologic toxicity; grade 3 or higher neurologic toxicity)
2. Intracranial response in patients with leptomeningeal metastases
3. Extracranial response as determined by RECIST and irRC
4. Leptomeningeal disease response as defined in section 11.4
5. Time to the first occurrence of extracranial disease progression, or death from any cause
6. Time to the first occurrence of intracranial disease progression, or death from any cause

Exploratory Endpoints: Genetic alterations

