In the Phase 1 study CA209004, ascending doses of nivolumab have been studied concomitantly with ascending doses of ipilimumab in subjects with unresectable or metastatic melanoma. In each arm in this multi-arm study, ipilimumab was administered once every 3 weeks for 4 doses with nivolumab administered once every 3 weeks for 8 doses. Starting at week 24, ipilimumab and nivolumab were administered once every 12 weeks for 8 doses. The three initial dose escalation cohorts consisted of Cohort 1 (nivolumab 0.3 mg/kg plus ipilimumab 3 mg/kg; n = 14), Cohort 2 (nivolumab 1 mg/kg plus ipilimumab 3 mg/kg; n = 17) and Cohort 3 (nivolumab 3 mg/kg plus ipilimumab 3 mg/kg; n = 6). Later, the study was amended to include Cohort 2a which evaluated nivolumab 3 mg/kg plus ipilimumab 1 mg/kg (n = 16) and Cohort 8 that represents an additional cohort of patients treated with nivolumab 1 mg/kg plus ipilimumab 3 mg/kg. The maintenance regimen for Cohorts 1-3 consisted of nivolumab q3 weeks x 4 then nivolumab plus ipilimumab q12 weeks x 8, while the maintenance regimen for Cohort 8 consisted of nivolumab 3 mg/kg q2 weeks until progression. The following dose limiting toxicities (DLTs) were observed in Cohort 1 - Grade 3 elevated AST/ALT (1 subject); in Cohort 2 - Grade 3 uveitis (1 subject) and Grade 3 elevated AST/ALT (1 subject) and in Cohort 3 Grade 4 elevated lipase (2 subjects) and Grade 3 elevated lipase (1 subject). Based on these data, Cohort 2 was identified as the maximum tolerated dose (MTD) and Cohort 3 exceeded the MTD. Among the 53 patients in the concurrent-regimen group, adverse events of any grade, regardless of whether they were attributed to the therapy, were observed in 98% of patients.

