Treatment-related adverse events of any grade were reported in 96.2% of patients, in pooled Cohorts 1-3 and 95.1% of Cohort 8. The drug-related skin select AE category was the most frequently reported category in all cohorts; rash and pruritus were the most frequently reported drug-related AEs in all cohorts. The most frequently reported drug-related AEs of any grade were rash (62.3%, Cohorts 1-3; 58.5%, Cohort 8), pruritus (56.6%, Cohorts 1-3; 46.3% Cohort 8), diarrhea (41.5%, Cohorts 1-3; 31.7%, Cohort 8), fatigue (41.5%, Cohorts 1-3; 41.5%, Cohort 8), lipase increased (26.4%, Cohorts 1-3; 14.6%, Cohort 8), AST increased (24.5%, Cohorts 1-3; 9.8%, Cohort 8), ALT increased (22.6%, Cohorts 1-3; 12.2%, Cohort 8), nausea (22.6%, Cohorts 1-3; 24.4%, Cohort 8), pyrexia (22.6%, Cohorts 1-3; 22.0%, Cohort 8), amylase increased (20.8%, Cohorts 1-3; 12.2%, Cohort 8). The only reported drug-related AE belonging to the pulmonary select AE category was pneumonitis; 3 (5.7%) subjects in Cohorts 1 to 3 and 1 (2.4%) subject in Cohort 8. Grade 3-4 events were reported in 1 subject each in Cohort 2a and Cohort 8. Treatment-related SAEs of any grade were reported in 58.5% of patients on pooled Cohorts 1-3 and 41.5 % of Cohort 8. The most frequently reported SAE in $\geq 5\%$ subjects included: ALT increased, AST increased, lipase increased, colitis, diarrhea, amylase increased, pneumonitis, and pyrexia. A total of 13 subjects (24.5%) in Cohorts 1-3 and 9 subjects (22.0%) in Cohort 8 discontinued therapy due to treatment-related adverse events. The majority of the deaths were due to disease progression in CA209004. One subject died due to drug-related enterocolitis. The only CNS treatment related AE reported in >10% of subjects was headache [11.3% Cohorts 1-3 (Grade 1-2); 12.2% Cohort 8 with 1 Grade 3-4 event (2.4%)]. A single case of radiation necrosis was observed in a subject who received SRT for progression in the brain

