6. DOSING DELAYS/DOSE MODIFICATIONS

The descriptions and grading scales found in the revised NCI Common Terminology Criteria for

Adverse Events (CTCAE) version 4.0 will be utilized for dose delays and dose modifications. A copy of the CTCAE version 4.0 can be downloaded from the CTEP website http://ctep.cancer.gov/protocolDevelopment/electronic_applications/ctc.htm.

There will be no dose modifications permitted. Dose reductions or dose escalations are not permitted.

Management Algorithms for Immuno-Oncology Agents

Immuno-oncology (I-O) agents are associated with adverse events that can differ in severity and duration than adverse events caused by other therapeutic classes. Nivolumab and ipilimumab are considered immuno-oncology agents in this protocol. Management algorithms have been developed to assist investigators in assessing and managing the following groups of adverse events: Gastrointestinal, Renal, Pulmonary, Hepatic, Endocrinopathies, Skin, and Neurological.

Early recognition and intervention are recommended according to the management algorithms; and in addition include ophthalmologic evaluations for any visual symptoms in order to evaluate for nivolumab or ipilimumab related uveitis.

The recommendations are to follow the algorithms in the nivolumab investigator brochure for immune related events; while the ipilimumab investigator brochure contains similar algorithms, the algorithms in the nivolumab brochure have been aligned to accommodate combinations as well as nivolumab monotherapy.

For subjects expected who require more than 4 weeks of corticosteroids or other immunosuppressants to manage an adverse event, consider the following recommendations

- Antimicrobial/antifungal prophylaxis per institutional guidelines to prevent opportunistic infections such as *Pneumocystis jiroveci* and fungal infections.
- Early consultation with an infectious disease specialist should be considered. Depending on the presentation, consultation with a pulmonologist for bronchoscopy or a gastroenterologist for endoscopy may also be appropriate.
- In patients who develop recurrent adverse events in the setting of ongoing or prior immunosuppressant use, an opportunistic infection should be considered in the differential diagnosis.

Additional details on the safety of nivolumab and ipilimumab , including results from clinical studies, are available in the IB.

Dose Delay Criteria

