13.6 Analysis of Secondary Endpoints

Safety and Tolerability: All adverse events recorded during the trial will be summarized for all patients having received one or more doses of ipilimumab and nivolumab. The data for each cohort will be summarized separately, although safety data may be combined, if appropriate. The proportions of patients with grade-3 or higher hematologic toxicities or grade-3 or higher neurologic toxicities will be presented with 90% exact binomial confidence intervals. The incidence of events that are new or worsening from the time of first dose of treatment will be summarized according to system organ class and/or preferred term, severity (based on CTCAE grade), type of adverse event, and relation to study treatment. Deaths reportable as SAEs and non-fatal serious adverse events will be listed by patient and tabulated by primary system organ class, and type of adverse event.

Intracranial/Extracranial Response: The proportion of patients with intracranial response of intraparenchymal brain metastases (CR or PR by RANO) will be presented with a two-sided, 90% exact binomial confidence interval. For a sample of 18 patients, the confidence interval will have maximum width of 0.42. Extracranial response rates (CR or PR) according to RECIST and irRC will be summarized. Rates will be accompanied by two-sided 90% exact binomial

confidence intervals. Cases where RECIST and irRC responses do not agree will be documented.

Leptomeningeal Disease Response: The proportion of patients with leptomeningeal disease response (CR or PR) will be presented with a two-sided, 90% exact binomial confidence interval. For a sample of 18 patients, the confidence interval will have maximum width of 0.42.

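### No per-patient rate of severe treatment-related toxicity is prespecified: the toxicity endpoint and its intervals cover only grade 3 or higher hematologic and neurologic events, whatever their cause

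*Combined protocol and SAP*

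**What the plan says.** The first secondary objective (Section 1.3) is to describe the toxicity of the combination. Section 13.1 turns this into secondary endpoint 1: "Toxicity by CTCAE criteria (grade 3 or higher hematologic toxicity; grade 3 or higher neurologic toxicity".

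Section 13.6 gives the analysis: "The proportions of patients with grade-3 or higher hematologic toxicities or grade-3 or higher neurologic toxicities will be presented with 90% exact binomial confidence intervals". No other safety quantity is given an interval.

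The same paragraph of 13.6 also plans a descriptive summary of all recorded adverse events. It covers the incidence of new or worsening events by system organ class and/or preferred term, by CTCAE grade, by type and by relation to treatment. SAEs are to be listed by patient and tabulated by organ class.

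Section 7.1 requires a CTCAE grade and a five-level attribution for adverse events. Section 2.2.3 reports what the combination did in CA209004; the SAE types it lists at 5% or more are "ALT increased, AST increased, lipase increased, colitis, diarrhea, amylase increased, pneumonitis, and pyrexia".

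**The concern.** The two classes chosen for the endpoint do not match where the protocol's own combination data place the common toxicity. In CA209004, "A total of 13 subjects (24.5%) in Cohorts 1-3 and 9 subjects (22.0%) in Cohort 8 discontinued therapy" because of treatment-related events. Section 6 requires permanent discontinuation for drug-related grade 3 colitis or pneumonitis, yet neither event would count toward the endpoint. A grade 3 neurologic deficit caused by meningeal progression could count.

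At stake is how the trial states its severe-toxicity rate. If the overall figure is not prespecified, its definition (which grades, which attribution levels, which denominator) is left to be chosen after the data are seen. The two rates that do carry intervals would say little about the expected immune-related harm.

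**Working it through.** **1. The plan's own precision figure.** Section 13.6 gives a maximum width of 0.42 for a 90% exact binomial interval at n = 18. It states this for the response rates, but the toxicity proportions use the same method. The limits for x of n are the Beta(x, n−x+1) quantile at 0.05 and the Beta(x+1, n−x) quantile at 0.95. The widest case is x = 9: 0.291 to 0.709, width 0.418. The figure is reproduced.

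**2. Where the reported events fall** (Section 2.2.3, CA209004):

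| Source list | Terms by site | Hematologic | Neurologic |
|---|---|---|---|
| SAE types in 5% or more (8) | liver enzymes 2, pancreatic enzymes 2, gut 2, lung 1, fever 1 | 0 | 0 |
| Most frequent drug-related AEs (10) | skin 2, gut 2, liver enzymes 2, pancreatic enzymes 2, fatigue 1, fever 1 | 0 | 0 |
| Dose-limiting toxicities (6 reports, Cohorts 1 to 3) | AST/ALT 2, lipase 3, uveitis 1 | 0 | 0 |

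The DLT row combines one grade 3 AST/ALT elevation in Cohort 1 with "Grade 3 uveitis (1 subject) and Grade 3 elevated AST/ALT (1 subject) and in Cohort 3 Grade 4 elevated lipase (2 subjects") and one further grade 3 lipase elevation in Cohort 3. The one drug-related death was from enterocolitis.

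**3. What is reported inside the endpoint classes.** Headache was the only CNS drug-related event above 10%: 11.3% in Cohorts 1-3, all grade 1-2, and 12.2% in Cohort 8, with one grade 3-4 case (2.4%). If 2.4% carried over, 18 × 0.024 = 0.43 patients would be expected, and the chance of none among 18 would be (1 − 0.024)^18 = 0.65. This is the contribution of one term. It is not a forecast of the endpoint.

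**4. Whether the planned tables can supply the overall rate.** One patient can appear in several rows. Section 2.2.3 shows the effect. In Cohorts 1-3 the ten frequent drug-related events sum to 62.3 + 56.6 + 41.5 + 41.5 + 26.4 + 24.5 + 22.6 + 22.6 + 22.6 + 20.8 = 341.4%, while 96.2% of patients had any treatment-related event. The largest row, 62.3%, gives only a lower bound. The by-patient SAE listing does not close the gap, because an event can be grade 3 or higher without meeting the seriousness criteria of Section 7.5.2.

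**5. Attribution of the neurologic rate.** Four places read together:
- Section 7.5.1 defines an adverse event without requiring causality.
- Section 2.1 lists cranial nerve palsies, seizures and encephalopathy as presenting features of the disease, and says death usually follows neurologic decline.
- Section 11.4 counts new neurologic symptoms from the meningeal disease as progression.
- Neither 13.1 nor the interval sentence in 13.6 limits the neurologic proportion to drug-related events.

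With no comparator arm, that proportion cannot separate drug from disease.

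**6. Precision of an added overall rate at n = 18.** 0/18 has an upper limit of 1 − 0.05^(1/18) = 0.153. 8/18 gives 0.244 to 0.659. With all 20 patients treated, the widest interval (10/20) is 0.302 to 0.698, width 0.396.

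**The case against.** The strongest reply is that Section 13.6 already handles most of this. Every adverse event is summarized by class, grade and relation, and SAEs are listed and tabulated. A grade 3 colitis will therefore appear with its attribution. The objective is to describe toxicity, and full tabulation does describe it. No stopping or decision rule uses this endpoint. This stands, and it limits the point to the named endpoint and its interval estimates.

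The classes are also not arbitrary. Neurologic safety is a natural focus in leptomeningeal disease. Section 2.2.1 calls neuropathy an important immune-related event, and Section 2.2.3 mentions one case of radiation necrosis. Section 6 has a discontinuation rule for thrombocytopenia, and Section 3.2.1 allows chemotherapy until shortly before treatment, so cytopenias are plausible. This is a reason to keep both proportions.

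It might be said that the word toxicity already implies drug-related. The protocol does not use it that way: Section 7.4 puts all adverse events on the toxicity forms.

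Three stronger readings are tempting and are not supported:
- **That the endpoint will come out near zero.** The available text gives no hematologic rate for the pair, and disease-related neurologic events could raise the neurologic rate.
- **That the endpoint will miss severe toxicity in about half the patients.** Section 2.2.3 says "Treatment-related SAEs of any grade were reported in 58.5% of patients on pooled Cohorts 1-3 and 41.5 % of Cohort 8", which would be 18 × 0.415 = 7.5 to 18 × 0.585 = 10.5 patients. These are SAEs of any grade, so they cannot be set against a grade 3 or higher endpoint. The text used here gives no overall grade 3 or higher rate.
- **That the toxicity objective is not met.** The descriptive tables meet it in part.

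**Conclusion.** The point holds in limited form. The toxicity endpoint and the only interval-bearing safety proportions cover two classes that contain 0 of 8 frequent SAE types, 0 of 10 frequent drug-related events and 0 of 6 DLT reports in the protocol's combination data. The neurologic proportion mixes drug and disease. No per-patient rate of severe treatment-related toxicity is prespecified, and the planned class or term tables cannot be summed to give one.

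The consequence is for reporting. The primary endpoint, sample size and decision rules are unaffected, and a reader should not infer that severe harm would go unreported.

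The conclusion assumes that CA209004 is a fair guide to which organs are affected. That was a melanoma study, whereas this trial enrolls any solid tumor with dosing by histology; Cohort 8 used the same mg/kg pair that Section 5.1 assigns to melanoma, small cell lung, breast and bladder cancer. The conclusion also rests on the part of Section 2.2.3 available for this review, which breaks off within the safety account.

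**What to change.** In Sections 13.1 and 13.6, add to secondary endpoint 1 the proportion of patients with any grade 3 or higher treatment-related adverse event. Define treatment-related as possible, probable or definite under Section 7.1, use the toxicity population of Section 13.8.1, and attach the 90% exact binomial interval already planned.

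Keep the hematologic and neurologic proportions. Report the neurologic one twice: overall, and limited to treatment-related events.

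Leave organ-level rates descriptive, by CTCAE system organ class. The Section 6 groups ("Gastrointestinal, Renal, Pulmonary, Hepatic, Endocrinopathies, Skin, and Neurological") would serve less well: they include no ocular and no named pancreatic group, so uveitis, and arguably lipase elevation, would have no row although both were DLTs. Organ-level intervals would also be imprecise: 1/18 gives 0.003 to 0.238.

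The cost is wording in two sections, one or two more intervals to report, and probably a less favourable stated toxicity rate. Grade and attribution are already recorded, so no new data, visits or patients are needed.

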13.2 Sample Size, Accrual Rate and Study Duration

Accrual of up to 20 patients may be required to achieve 18 evaluable patients.

The primary endpoint is the rate of overall survival at 3 months (OS3). Any patient whose vital status at 3 months cannot be determined will be counted as having died. A Simon two-stage design will be used to compare a null hypothesis OS3 of 18% against an alternative of 43%. Nine patients will be enrolled in the first stage. If 0 or 1 patients are alive at 3 months, the trial will be stopped early. If 2 or more patients are alive at 3 months, we will enroll an additional 9 patients. If at least 6 patients among the total of 18 patients are alive at 3 months, then the treatment would be promising in the cohort. This design has a type-I error of 8% (target 10%) and power of 86% (target 85%). If the null hypothesis is true, then the probability is 0.50 of stopping at the end of the first stage.

In addition, we will assess for the primary outcome of any histologic, molecular subtype (e.g., ER/PR-positive, HER2-positive breast cancer, EGFR mutant lung cancer) with 6 patients

enrolled for that particular subtype. If no patient within a particular histologic subtype has achieved the primary outcome, then patients with that histology will no longer be eligible to enroll in the trial. Under the alternative hypothesis (i.e., OS3 = 43%), the probability is 0.03 of observing no patients with OS3 among 6 patients.

The accrual rate is based on our institutional patient volume of 3-4 patients per month with leptomeningeal carcinomatosis seen in our multidisciplinary brain metastasis clinic. We estimate that 1-2 patients per month will be eligible for this protocol. Therefore, 20 patients will be accrued within 10-20 months. Based on six months of follow-up (median survival of patients is approximately 2-4 months), total study duration will be 24 months.

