The overall safety experience with nivolumab, as a monotherapy or in combination with other therapeutics, is based on experience in approximately 4,000 subjects treated to date. For monotherapy, the safety profile is similar across tumor types. The only exception is pulmonary inflammation adverse events (AEs), which may be numerically greater in subjects with NSCLC, because in some cases, it can be difficult to distinguish between nivolumab-related and unrelated causes of pulmonary symptoms and radiographic changes. There is no pattern in the incidence, severity, or causality of AEs to nivolumab dose level. In several ongoing clinical trials, the safety of nivolumab in combination with other therapeutics such as ipilimumab, cytotoxic chemotherapy, anti-angiogenics, and targeted therapies is being explored. Most studies are ongoing and, as such, the safety profile of nivolumab combinations continues to evolve. The most advanced combination under development is nivolumab + ipilimumab in subjects with melanoma. Thus far, the combination of both agents results in a safety profile with similar types of AEs as either agent alone, but in some cases with a greater frequency.

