As astounding as these developments are, there remains one group of patients who remain ineligible for virtually every therapeutic trial, those with leptomeningeal disease (LMD). While any malignancy can metastasize to the leptomeninges, this most commonly occurs with lung cancer, breast cancer and melanoma. Approximately 5-8% of patients with cancer develop leptomeningeal carcinomatosis¹. As visceral metastatic disease is better controlled and patients are surviving longer, LMD is being diagnosed more frequently. The median survival of patients with LMD without treatment is dismal, typically 4-6 weeks. Novel therapies are needed to improve outcomes in patients with LMD. The absence of effective therapies, and more importantly, access to treatment as part of clinical trials is a great unmet need in cancer.

A recent study demonstrated that ipilimumab has activity in patients with brain metastases; however and not surprisingly, patients with LMD were excluded from this study. In our experience at Massachusetts General Hospital (MGH) Cancer Center, we have observed 2 clinical responses in the approximately 10 patients with melanoma and LMD who have received ipilimumab. Moreover there was one published report of describing a patient with leptomeningeal disease from melanoma having a complete response after receiving ipilimumab¹⁶. Furthermore, in a separate PI-initiated trial (DF/HCC #16-153), an interim analysis of 18 patients with LMD treated with pembrolizumab showed that primary endpoint has been met, and more than 8 patients survived more than 3 months. The role of immunotherapy has not been systematically explored in this patient population, and based on our limited but encouraging experience with our patients, we have proposed a Phase II trial of ipilimumab plus nivolumab in patients with LMD, using a dose schedule that has demonstrated efficacy in other tumors. This trial offers a unique opportunity to systematically study LMD at the genomic and immune microenvironmental levels before and during therapy.

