3.2 Exclusion Criteria

- 3.2.1 Participants who have had chemotherapy, targeted small molecule therapy or study therapy within 5 days of protocol treatment, or those who have not recovered (i.e., \leq Grade 1 or at baseline) from adverse events due to agents administered more than 2 weeks earlier. Subjects with \leq Grade 2 neuropathy are an exception to this criterion and may qualify for the study. If subject received major surgery, they must have recovered adequately from the toxicity and/or complications from the intervention prior to starting therapy.
- 3.2.2 Participants who are receiving any other investigational agents.
- 3.2.3 Patients should be excluded if they have an active, known or suspected autoimmune disease. Subjects are permitted to enroll if they have vitiligo, type I diabetes mellitus, residual hypothyroidism due to autoimmune condition only requiring hormone replacement, psoriasis not requiring systemic treatment, or conditions not expected to recur in the absence of an external trigger
- 3.2.4 Patients should be excluded if they have a condition requiring systemic treatment with either corticosteroids (> 10 mg daily prednisone equivalents) or other immunosuppressive medications within 14 days of study drug administration. Inhaled or topical steroids and adrenal replacement doses > 10 mg daily prednisone equivalents are permitted in the absence of active autoimmune disease. Subjects are permitted to use topical, ocular, intra-articular, intranasal, and inhalational corticosteroids (with minimal systemic absorption). Physiologic replacement doses of systemic corticosteroids are permitted, even if > 10 mg/day prednisone equivalents. A brief course of corticosteroids for prophylaxis (eg, contrast dye allergy) or for treatment of non-autoimmune conditions (eg, delayed-type hypersensitivity reaction caused by contact allergen) is permitted.
- 3.2.5 As there is potential for hepatic toxicity with nivolumab or nivolumab/ipilimumab combinations, drugs with a predisposition to hepatotoxicity should be used with caution in patients treated with nivolumab-containing regimen.

- 3.2.6 Patients should be excluded if they have had prior systemic treatment with a combination of anti-CTLA4 antibody and anti-PD1/PDL1 antibody. Prior treatment with single agent anti-CTLA4, anti-PD1 or anti-PDL1 antibody is allowed.
- 3.2.7 Has a known history of active TB (Bacillus Tuberculosis)

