13.8.2 Evaluation of the Primary Efficacy Endpoint

To be included in the assessment of the primary objective, patients need to receive at least one cycle.

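### Meeting the 6/18 rule for 3-month survival rejects only an unsourced 18% and shows no gain over one checkpoint inhibitor, and the one-cycle rule in 13.8.2 can lift the false-go rate above its 10% target

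*Combined protocol and SAP*

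**What the plan says.** **The test.** Section 13.2: "A Simon two-stage design will be used to compare a null hypothesis OS3 of 18% against an alternative of 43" per cent. Nine patients enter first, and the trial stops if 0 or 1 is alive at 3 months. Otherwise nine more enter: "If at least 6 patients among the total of 18 patients are alive at 3 months, then the treatment would be promising in the cohort". The stated type I error is 8% (target 10%), the power 86% (target 85%), and the probability of early stopping under the null 0.50. No source or population is given for 18% or 43%.

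**The single-agent result.** Section 2.3 describes "an interim analysis of 18 patients with LMD treated with pembrolizumab", which "showed that primary endpoint has been met, and more than 8 patients survived more than 3 months". It is offered as part of the rationale, which ends "based on our limited but encouraging experience with our patients, we have proposed a Phase II trial of ipilimumab plus nivolumab". Section 13 does not mention it.

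**Who is counted.** Section 13.8.2: "To be included in the assessment of the primary objective, patients need to receive at least one cycle". Section 5.1 sets the cycle at 6 weeks, with 8 weeks only for some maintenance phases. Section 13.2 allows up to 20 patients to be accrued to obtain 18 evaluable. Sections 13.2 and 13.5 count unknown vital status at 3 months as death.

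**Context.** Section 3.2: "Prior treatment with single agent anti-CTLA4, anti-PD1 or anti-PDL1 antibody is allowed". Section 2.2.2 says that the combination gives "similar types of AEs as either agent alone, but in some cases with a greater frequency".

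**The concern.** The decision turns on the word *promising*, and its only stated comparator is 18%. The protocol's own background contains a 3-month survival figure for a PD-1 antibody in leptomeningeal disease that is well above 18%. A reader of a positive result could take it as support for giving two drugs when the rule asks only that 18% be beaten. Because the combination brings some adverse events more often than either agent alone, that misreading matters.

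The analysis set adds a second problem. With a survival endpoint, requiring a completed 6-week cycle removes patients because they died early. Both the estimate and the count of successes then refer to a selected group, while the 18% null carries no such condition.

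**Working it through.** **1. Reproduce the plan's figures.** For a true rate p, the probability of meeting the rule is the sum over x = 2 to 9 of P(Bin(9, p) = x) × P(Bin(9, p) ≥ 6 − x).

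- Early stopping at 18%: 0.82⁹ + 9 × 0.18 × 0.82⁸ = 0.168 + 0.331 = 0.499 (stated 0.50).
- Type I error at 18%: 0.0845 (stated 8%).
- Power at 43%: 0.842 (stated 86%, target 85%). Ignoring the first stage gives 0.857, so the stated power is slightly high. This is a side point.

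**2. The pembrolizumab figure.** More than 8 of 18 means at least 9/18 = 50%.

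- Exact (Clopper-Pearson) 90% interval for 9/18: 0.291 to 0.709.
- P(Bin(18, 0.18) ≥ 9) = 0.002, so that result is itself hardly compatible with 18%.
- The interval includes 43% and also the cut-off, 6/18 = 33%.

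**3. How often the current rule is met.**

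| True OS3 | Probability of a pass |
|---|---|
| 18% | 8.5% |
| 29% (lower 90% limit for 9/18) | 42% |
| 35% | 63% |
| 43% | 84% |
| 50% (9/18 taken at face value) | 94% |

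A regimen that adds nothing to a single-agent OS3 anywhere from 29% to 50% would pass between 42% and 94% of the time.

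**4. Where 18% might come from.** Section 2.1 gives an untreated median of 4-6 weeks. If survival is exponential (an assumption) and 3 months is 13 weeks, OS3 is 0.5^(13/4) = 11% to 0.5^(13/6) = 22%. The 2-4 month median used in 13.2 to plan study duration gives 0.5^(3/2) = 35% to 0.5^(3/4) = 59%. So 18% fits an untreated population, but the plan does not say that this is its origin.

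**5. The one-cycle rule.** Assume exponential survival with OS3 = 18%, and read one cycle as surviving 6 weeks.

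- Alive at 6 weeks: 0.18^(6/13) = 0.453.
- OS3 among those alive at 6 weeks: 0.18 / 0.453 = 0.397.
- Per patient under the null: dead before 6 weeks 0.547; dead between 6 weeks and 3 months 0.453 − 0.18 = 0.273; alive at 3 months 0.18.

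Only about 20 × 0.453 = 9 of 20 registered patients would complete a cycle, so full exclusion of early deaths cannot produce 18 evaluable patients within the cap. The usable case is limited replacement: patients are taken in order, the first two early deaths are replaced, later ones count as failures, and the 2/9 and 6/18 rules apply to those counted. The exact probability of a pass at OS3 18% is then 0.132. Allowing one replacement per stage gives 0.129. Both are about 13%, against 0.0845 without replacement. Taking 3 months as 12 weeks leaves both at about 13%.

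**6. What a higher bar would cost.** Exact two-stage results:

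| Design | Type I error | Power | Early stopping under null | Pass if OS3 is 50% |
|---|---|---|---|---|
| 50% v 75%: at least 5/9, then 14/21 | 8.9% | 85.3% | 0.50 | 8.9% |
| 35% v 60%: at least 4/10, then 11/22 | 9.95% | 85.8% | 0.51 | 56% |
| 30% v 55%: at least 2/7, then 10/22 | 8.8% | 85.2% | 0.33 | 72% |
| 9+9 kept, 9/18 (30% v 55%) | 6.0% | 75% | 0.20 | 59% |
| 9+9 kept, 10/18 (35% v 60%) | 6.0% | 74% | 0.12 | 41% |
| 9+9 kept, 13/18 (50% v 75%) | 4.8% | 72% | 0.02 | 4.8% |

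**The case against.** The trial makes no comparison with a single agent. Section 1.2 sets out to estimate overall survival in one arm, and 13.2 does say what is tested: 18% against 43%. No single-arm trial of about 20 patients could separate two drugs from one. The benchmark is one clause about another trial, interim and without case mix. This trial also admits patients already given a single checkpoint inhibitor, for whom pembrolizumab survival may not be the right reference.

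All of this stands, and it rules out a stronger reading that a reader might infer: that 43% and 6/18 lie below an established single-agent rate, so the design is wrong and the null must be raised. The 29% to 71% interval covers both 43% and 33%, and Section 2.3 does not establish a single-agent rate. Nor would a higher null cure the problem cheaply. The designs built on 30% or 35% still pass a no-gain regimen at 50% in 41% to 72% of cases, and keeping 9+9 with a higher final cut-off gives up most of the early stopping.

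What the objection does not answer is that neither rate has a source, that Section 13 is silent on a result the protocol relies on elsewhere, and that the reach of a pass is left for the reader to guess.

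On the analysis set, one could read receiving a cycle as merely starting one. The text does not say so. The allowance of 20 patients to obtain 18 evaluable suggests that some treated patients may be replaced.

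**Conclusion.** The point holds in a limited form. The design tests 18% against 43% essentially as stated. A pass rejects 18% and nothing more: it occurs 42% of the time at a true OS3 of 29%, 84% at 43% and 94% at 50%, so by itself it is no evidence of gain over one checkpoint inhibitor. These probabilities are exact. Which of them applies depends on a single-agent rate that the documents do not fix.

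The one-cycle rule is a separate weakness. If it excludes deaths before 6 weeks, OS3 is inflated relative to the 18% null, and replacing up to two such deaths takes the false-go rate from 8.5% to about 13%. This rests on exponential survival and on that reading of 13.8.2.

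**What to change.** 1. **Section 13.8.2:** include every patient who starts treatment in the OS3 analysis and count early deaths as failures, without replacement. This matches the rule in 13.2 and 13.5 that unknown vital status counts as death. It needs no extra patients and restores the 8.5% type I error.
2. **Sections 13.2 and 13.5:** give the source and population of 18% and 43%. State that *promising* means only that an OS3 of 18% is rejected, and that it does not show improvement over single-agent therapy.

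The cost is a less favourable OS3 estimate and a narrower claim after a positive result.

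**Optional, for the sponsor to weigh:** raise the null or the final cut-off. With the plan's 10% and 85% targets and 25-point step, this takes 21 or 22 evaluable patients, which is 3 or 4 more (about 2 to 4 months at 1-2 per month). Keeping 9+9 and raising only the final cut-off adds no patients, but power falls to 72-75% and first-stage stopping under the null falls from 0.50 to between 0.02 and 0.20. The choice of null would need a single-agent rate that the documents do not supply.
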